6 STUDY ASSESSMENTS

6.1 STUDY ASSESSMENTS

Participants will complete measures at three time points: before the first group session, after the last group session and before the focus group approximately six weeks after the last group session.

6.2 LONG TERM FOLLOW UP ASSESSMENTS

Participants will be invited to take part in an hour-long focus group approximately six weeks after the therapeutic group has ended. This focus group will be facilitated by a researcher, who may be LD-CAMHS clinician, to reduce the impact of a social desirability bias in participants' responses. Parents and education staff will attend separate focus groups. There will be no further follow-up after the focus group. Participants will be asked to complete the follow-up measures just before the focus group takes place. If participants do not attend the focus group, questionnaires will be posted to their home address with a return envelope provided, or they may return them to their LD-CAMHS clinician or participating school.

7 DATA COLLECTION

7.1 MEASURES

Demographic Data

A questionnaire will ask participants:

- their child's age, gender and diagnoses,
- their own age and gender,
- their attained education level and occupational status,

- whether the parent or education staff member has attended any relevant training or psychoeducation groups,
- whether the person is the primary caregiver for the child and if there is another significant caregiver available to the child (if a parent; e.g. second residential parent, non-residential parent, residential grandparent)
- number of years they have been in their role (if education staff).

Depression Anxiety and Stress Scale -21 item (DASS-21)

The DASS-21 is the short form measure of the Depression Anxiety and Stress Scale (Lovibond & Lovibond, 1995). The DASS-21 is widely used and has normative data available derived from a UK population sample (Henry & Crawford, 2005). The DASS-21 has three subscales of depression, anxiety and stress, with an underlying general factor of psychological distress (Henry & Crawford, 2005). The scale has been shown to have excellent internal reliability ($\alpha = 0.93$) and good convergent validity (Henry & Crawford, 2005). The DASS-21 has been chosen above the General Health Questionnaire-12 due to the criticism levelled at it regarding the possible impact of response bias on its psychometric integrity (Hankins, 2008) and as its suggested factors of anxiety/depression, social dysfunction and loss of confidence are not what is hoped to be captured by a measure of psychological distress in this study (Romppel et al., 2013).

Copenhagen Burnout Inventory (CBI; Borritz et al., 2006; for Education Staff only).

The CBI is a nineteen-item measure consisting of three subscales of personal, client-related and work-related burnout. Burnout has been conceptualised as emotional, mental and physical exhaustion related to chronically high levels of emotional demand at work (Schaufeli & Greenglass, 2001). Burnout is included within this study for education staff as it is thought that burnout may capture a different aspect of the impact of the demands of working in a school for children with special educational needs beyond a measurement of psychological distress, and as burnout may feel more acceptable for education staff to report than psychological distress. The measure was developed in response to criticism of the Maslach Burnout Inventory, and has been validated for use with a general Danish workforce sample and samples of teachers from New Zealand and Italy (Borritz et al., 2006; Fiorilli et al., 2015; Milfont et al., 2008). The measure has been shown to have good internal reliability and construct validity (Borritz et al., 2006; Milfont et al., 2008).

Challenging Behaviour Self-Efficacy Scale (CBSES)

Hastings and Brown (2002a) developed the CBSES as a five-item measure of self-efficacy related to managing challenging behaviours, with items such as "How confident are you in dealing with the challenging behaviours of the child/children you care for". The measure is scored with a seven-point likert scale. In a sample of parents of children with autism and challenging behaviour, there was excellent internal reliability for mothers ($\alpha = 0.94$) and fathers ($\alpha = 0.92$). The measure has since been subject to a confirmatory factor analysis with Korean and US samples (Oh & Kozub, 2010), which identified a one factor model with adequate model fit and excellent internal reliability.

Comprehensive Assessment of Acceptance and Commitment Therapy Processes (ComPACT)

ComPACT is a recently developed 23 item ACT process measure (Francis et al., 2016). The measure was developed by consensus from experts, with an item pool derived from 11 other ACT process measures. It was developed due to the lack of a questionnaire that measured all aspects of ACT. For example, the Acceptance and Action Questionnaire (AAQ-II) has been argued to capture experiential avoidance and to neglect committed action (Francis et al., 2016). The ComPACT measure has demonstrated adequate internal consistency and good convergent and concurrent validity (Francis et al., 2016).

Workshop Evaluation Measure (WEM)

A brief measure will be devised on the basis of a previous social validity measure for an ACT based workshop (Bethay et al., 2013), with items such as "I have been consistently practicing the techniques and principles that I learned in the workshop" and "the workshop was interesting

and enjoyable", rated on a seven point Likert scale ranging from completely disagree to completely agree. Open-ended items such as "what was the most helpful part of the workshop?" and "what was the least helpful part of the workshop?" will additionally be included to allow participants to flexibly express their experience of the intervention. This measure will be completed at the end of the third workshop session. Finally, all of these measures are free to use, and it is estimated that it will take participants up to fifteen minutes to complete this questionnaire battery.

The following table details when participants will complete each questionnaire.

Participant Type	Group Session 1	Group Session 3	Focus Group/Postal
Parents	
 Demographics DASS-21 CBSES ComPACT 	
 DASS-21 CBSES ComPACT WEM 	
 DASS-21 CBSES ComPACT
Education Staff	
 Demographics DASS-21 CBI CBSES ComPACT 	
 DASS-21 CBI CBSES ComPACT WEM 	
 DASS-21 CBI CBSES ComPACT

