2.2.2 Secondary Endpoints

The secondary outcome measures are as follows:

- The Challenging Behaviour Self-Efficacy Scale (CBSES)

- Copenhagen Burnout Inventory (CBI) (Education staff only)
- Comprehensive Assessment of Acceptance and Commitment Therapy Processes (ComPACT)
- Workshop Evaluation Measure (WEM)

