5.2.1 Withdrawal of Study Participants

Participants are free to withdraw from the study at any point or a participant can be withdrawn by the Investigator. If withdrawal occurs, the primary reason for withdrawal will be documented in the participant's case report form, if possible. The participant will have the option of withdrawal from

- (i) all aspects of the trial but continued use of data collected up to that point
- (ii) all aspects of the trial with removal of all previously collected data

Participants who do not attend one or more of the group sessions will be welcome to attend the remaining sessions if they so wish but will be excluded from any relevant analyses. Participants may take part in the focus group if they have attended at least one group session.

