8 STATISTICS AND DATA ANALYSIS

8.1 SAMPLE SIZE CALCULATION

Power calculations were performed utilising G-Power 3.1 (Faul et al., 2007). The statistical analysis was set to be a with a within-between interaction, with two groups and three measurement points. The alpha level was set to 0.05 and power to 0.80, as per convention (Cunningham & McCrum-Gardner, 2007). The effect size previously reported for psychological distress in a similar study (McConachie et al., 2014) was medium to large. To be conservative, the power calculation for this study was performed with a medium effect size ($f=0.25$), which suggested a total sample size of 28 participants. Therefore, this study will aim to have four groups with ten participants each. This would mean recruiting 40 participants, with the expectation that 12 would be lost to attrition.

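### Someone who misses session 3 has no stated way to give a workshop rating (WEM) or post-workshop scores, so the WEM may be selective, and section 5.2.1 would exclude their scores anyway

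*Combined protocol and SAP*

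**What the plan says.** Section 2.2.2 lists the WEM among the secondary outcomes. Section 7.1 gives its timing: "This measure will be completed at the end of the third workshop session". It has items on a seven-point scale and open questions, one of them about the least helpful part of the workshop.

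Section 6.1 sets three assessment times: "before the first group session, after the last group session and before the focus group approximately six weeks after the last group session". The columns of the schedule table in section 7.1 are headed "Participant Type Group Session 1 Group Session 3 Focus Group/Postal". The WEM appears only in the session 3 column, beside the post-workshop DASS-21, CBSES and ComPACT, and the CBI for education staff. Only the third column mentions post, and its contents do not include the WEM.

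Section 6.2 describes the postal route: "If participants do not attend the focus group, questionnaires will be posted to their home address with a return envelope provided". It also allows return through the clinician or school. Both routes concern the six-week measures.

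Section 5.2.1 says that people who miss one or more sessions "will be welcome to attend the remaining sessions if they so wish but will be excluded from any relevant analyses". It then adds: "Participants may take part in the focus group if they have attended at least one group session".

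Section 8.1 plans to recruit 40 "with the expectation that 12 would be lost to attrition". Section 8.2 commits to reporting the percentage of missing data and to imputation, after examining the mechanism if 5% or more is missing.

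**The concern.** Take a participant who attends sessions 1 and 2, misses session 3 and does not withdraw. The plan can send that person the six-week scales and can invite them to the focus group. It never asks them to rate the workshop, and it gives no route for a post-workshop score.

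For the WEM, the people out of reach may include those who found the workshop unhelpful or too demanding, and the question on its least helpful part does not reach them either. The reported mean would then describe those present at session 3, not those who started. This sits badly with the realist framework in section 3, which is interested in differences between participants, and with the decision to admit partial attenders to the focus group.

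For the outcome scales, the analysis is a repeated-measures ANOVA over three time points. A missing middle score leaves an incomplete case that must be imputed or dropped, even when baseline and six-week scores are in hand.

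**Working it through.** **1. The plan's own figures.** Section 8.1 gives a within-between interaction with k = 2 groups, m = 3 measurements, f = 0.25, alpha 0.05 and power 0.80. It states neither the correlation between measurements nor a sphericity correction, so rho = 0.5 and epsilon = 1 are assumed here.

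- Noncentrality at N = 28: f² × N × m / (1 − rho) = 0.0625 × 28 × 3 / 0.5 = 10.5.
- Degrees of freedom: (k − 1)(m − 1) = 2 and (N − k)(m − 1) = 52.
- Power is 0.812 at N = 28 and 0.778 at N = 26, so 28 reproduces.
- Attrition: 12/40 = 30%, and 28 / (1 − 0.30) = 40, which matches the recruitment target.

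**2. Routes for a person absent at session 3.**

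| Data | When scheduled | Stated route for an absentee |
|---|---|---|
| WEM | End of session 3 only | None |
| Post-workshop DASS-21, CBSES, ComPACT, CBI (staff) | Session 3 column | None |
| Six-week DASS-21, CBSES, ComPACT, CBI (staff) | Focus group or post | Post, or return to clinician or school |
| Focus group | Six weeks after the last session | Open after one session attended |

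**3. Effect on the WEM mean.** Let d be the share with no rating. Then responder mean − mean of everyone = d × (responder mean − non-responder mean).

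The documents give no value for d at session 3 and no expected ratings, so both are varied. Entries are the shift in points on the seven-point scale.

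| Gap (responders minus non-responders) | d = 0.10 | d = 0.20 | d = 0.30 |
|---|---|---|---|
| −1 | −0.10 | −0.20 | −0.30 |
| 0 | 0 | 0 | 0 |
| +1 | +0.10 | +0.20 | +0.30 |
| +2 | +0.20 | +0.40 | +0.60 |

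As an outer limit, take d = 0.30 and an assumed responder mean of 6. If every missing rating were 1, the overall mean would be 0.7 × 6 + 0.3 × 1 = 4.5. If every one were 7, it would be 0.7 × 6 + 0.3 × 7 = 6.3.

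**4. Effect on a post-workshop score.** Assume that those analysed improve by 0.5 SD and that d = 0.30. If the others do not change, the mean over everyone is 0.7 × 0.5 + 0.3 × 0 = 0.35 SD, and the analysed figure is 0.15 SD too high. If the others improve by 0.5 SD, the error is zero. If they improve by 0.75 SD, the overall mean is 0.575 SD and the analysed figure is 0.075 SD too low.

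**5. Whether collection alone would cure it.** Suppose the session 3 pack were posted and returned. Section 5.2.1 would still keep the person out of the relevant analyses because a session was missed. The same rule reaches someone who attends session 3 after missing an earlier session, although that person can complete the pack in the room. Section 8.2 does not say whether imputation covers people excluded in this way.

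**The case against.** The strongest objection is that, for the outcome scores, the timing of collection is not the deciding cause. The exclusion rule in section 5.2.1 is enough to remove partial attenders whatever is collected. This stands, and a remedy that only posts the pack would fail for the scores.

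A reader might infer that the WEM and the scores will look too favourable. The documents do not support that. They give no reasons for missing sessions, and the working shows that the error can be zero or reversed. For the WEM an upward shift is plausible; for the symptom scores there is no particular argument for a direction.

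A reader might also infer that 30% of starters will give no WEM. The 12 of 40 is total attrition with no timing. Section 3 places six of the nine active weeks after the sessions, so some of the loss may come later. A recruit who attends no session has nothing to rate, and a person who withdraws from all aspects of the trial should not be approached. The number within reach may be well below 12.

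Nor are session 3 attenders all full completers, since section 5.2.1 welcomes back people who missed a session. Absence is not the same as lack of benefit, and attenders who did not benefit can still say so. Section 6.1 does not itself require the second set to be completed in the room, although the table ties it to session 3 and names no other route.

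The plan has partial safeguards: reporting of missing data, imputation, a recorded reason for withdrawal where possible, posted six-week scales and an open focus group. They would make some of the loss visible. None supplies a missing WEM, which is measured once, has no earlier or later value to inform imputation, and has open comments that cannot be imputed.

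Finally, no stated objective or hypothesis concerns acceptability. This limits the weight of the WEM part but does not remove it, because the WEM is a listed endpoint and the remedy is cheap.

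**Conclusion.** The gap in collection is real. No stated route obtains a WEM or post-workshop scores from a participant who attended at least one session, missed session 3 and has not withdrawn. The WEM results may therefore be selective, and are plausibly too favourable if dissatisfied people tend to stop earlier; the direction is not established.

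The size cannot be fixed from the documents. Taking the full 30% as an upper bound for the share missing at session 3, each 1-point gap between responders and non-responders shifts the mean by 0.3 points. The loss, and the shift, shrink in proportion if fewer are missing.

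For the outcome scores, the exclusion rule in section 5.2.1 is itself sufficient to cause the omission, so collection and analysis must change together. This is a worthwhile, inexpensive improvement and not a fatal flaw. It should be settled before the first group runs, because ratings not collected at the time cannot be recovered later.

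**What to change.** 1. In sections 6.1, 6.2 and 7.1, including the schedule table, extend the existing postal or return route to the session 3 pack (WEM and post-workshop scales). Offer it to anyone who attended at least one session, missed session 3 and has not withdrawn, and send it soon after that session.
2. Report the WEM for all who attended at least one session, by number of sessions attended, with the response rate beside it.
3. Amend section 5.2.1 so that these participants' WEM and outcome scores are included in the analysis, with full attenders only as a sensitivity analysis.
4. Reconcile section 5.2.1 with section 8.2 by stating whose missing scores are imputed.

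The cost is some postage and a short amendment, using a procedure the protocol already has. Some forms will be completed at home a few days later than those completed in the room, so the completion date should be recorded. Not everyone will reply, so the selection is reduced and made visible but not removed.

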7.2 SOURCE DATA DOCUMENTATION

Source documents are those in which information is recorded and documented for the first time.

Source	Data
Paper consent form	Participant written informed consent
Paper participant contact information sheet	Participant contact details and GP contact details
Medical notes – paper and electronic (Trak)	Note from direct care team clinician recording date of provision of participant information sheet, and relevant information regarding participation in the study.
School files/notes – paper and/or electronic	Note from education staff recording date of provision of participant information sheet and relevant information regarding participation in the study.
Audio file on an NHS audio recorder	Audio recording of focus groups
Paper questionnaires	Questionnaire data
Electronic database	Electronic Anonymised Questionnaire Data

Electronic word files	Anonymised transcripts of focus groups
-----------------------	--

8 STATISTICS AND DATA ANALYSIS

8.1 SAMPLE SIZE CALCULATION

Power calculations were performed utilising G-Power 3.1 (Faul et al., 2007). The statistical analysis was set to be a with a within-between interaction, with two groups and three measurement points. The alpha level was set to 0.05 and power to 0.80, as per convention (Cunningham & McCrum-Gardner, 2007). The effect size previously reported for psychological distress in a similar study (McConachie et al., 2014) was medium to large. To be conservative, the power calculation for this study was performed with a medium effect size ($f=0.25$), which suggested a total sample size of 28 participants. Therefore, this study will aim to have four groups with ten participants each. This would mean recruiting 40 participants, with the expectation that 12 would be lost to attrition.

8.2 PROPOSED ANALYSES

Summary Measures Reported

The mean, standard deviation and range of the demographic variables and dependent variables will be reported. The percentage of missing data across the measures will also be reported.

Methods of Analysis

Regarding quantitative data, the statistical analysis will be completed using SPSS software. Data will be explored to ensure that test assumptions are met. Each dependent variable will then be analysed with repeated measures analyses of variance (ANOVA) with a within-between interaction, with significant effects further evaluated appropriately.

Regarding qualitative data, the focus group interview transcripts will be analysed with thematic analysis, as per Braun and Clarke (2006).

Management of Missing Data

Should the level of missing data be minimal (<5%), the data will be assumed to be missing at random and a suitable method of imputation (most likely multiple imputation due to the small sample size) will be used to manage this appropriately.

Should a higher level of missing data occur, the missing data will be analysed to examine whether it is missing at random or not. A suitable method of imputation will then be used.

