Considering the currently available research, it appears that there is a developing evidence base for ACT and mindfulness-based interventions for parents, teachers and support staff, and for mindfulness-based PBS for parents and support staff. However, it appears that there is yet to be a quantitatively evaluated parent ACT workshop or combined ACT and PBS-based intervention. ACT and PBS are theoretically paired well together, in the context of their values focus and emphasis on increasing quality of life in a meaningful way. Given that parents and teachers both appear in need of access to these psychological interventions to support them in their distress and in their implementation of PBS, in this study, parents and teachers of CYP-ID will participate in a mixed methods study evaluating the effectiveness and mechanisms of an ACT and PBS based group workshop. The workshop format should fit well within tier one and two mental health services and provide a sustainable way to systemically improving the wellbeing of children and young people with IDs and the caregivers around them.

Quantitative Research Questions

- Is an ACT and PBS based group workshop ("the intervention") effective in reducing the psychological distress experienced by parents and teachers who work with children with IDs?
- Is the intervention effective in increasing parents and education staff self-efficacy in managing children's challenging behaviour?
- Is the intervention effective in reducing education staff's self-reported experience of burnout?
- Is there a significant change in the parents and education staff Acceptance and Commitment Therapy processes?

Qualitative Research Question

- In which contexts and through which mechanisms does the group work to achieve these outcomes?

Study Hypotheses

- The intervention will be effective in significantly reducing the psychological distress self-reported by parents and teachers who work with children with IDs.
- The intervention will be effective in significantly increasing parents and education staff self-reported self-efficacy in managing children's challenging behaviour.
- The intervention will be effective in significantly reducing education staff's self-reported experience of burnout.

Study Risks and Benefits

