2 STUDY OBJECTIVES

2.1 OBJECTIVES

2.1.1 Primary Objective

- To evaluate whether an ACT and PBS based workshop ("the intervention") is effective in reducing the psychological distress experienced by parents and education staff who work with children with Intellectual Disability.

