4 STUDY POPULATION

4.1 NUMBER OF PARTICIPANTS

- We will aim to recruit approximately 40 participants to the study (10 participants allocated to four groups).
- Number of sites involved: 8 (LD-CAMHS and up to 7 schools for children with special educational needs).
- Length of recruitment period: Estimated at approximately six to eight months.

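### Does section 8.2 need to name the between-subjects factor and say whether time or the interaction decides each hypothesis?

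*Combined protocol and SAP*

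**What the plan says.** Section 8.2 (Methods of Analysis) covers all quantitative testing in one sentence: "Each dependent variable will then be analysed with repeated measures analyses of variance (ANOVA) with a within-between interaction", and then "with significant effects further evaluated appropriately". It does not identify the between factor and does not say which effect decides a hypothesis.

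Section 8.1 sizes the study for a "within-between interaction, with two groups and three measurement points". It uses f = 0.25, alpha 0.05 and power 0.80, and arrives at 28 participants, raised to 40 to allow for 12 lost. It does not say which two groups are meant. Section 4.1 describes the workshop groups as "10 participants allocated to four groups". No control arm or randomisation is described. The only two-level grouping is participant type, parent or education staff, in the measures table of section 7.1.

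The aims are worded as change. The primary objective (section 2.1.1) asks whether the workshop "is effective in reducing the psychological distress experienced by parents and education staff who work with children with Intellectual Disability". The first hypothesis in section 1.1 reads "The intervention will be effective in significantly reducing the psychological distress self-reported by parents and teachers who work with children with IDs". The question on ACT processes is "Is there a significant change in the parents and education staff Acceptance and Commitment Therapy processes".

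Two secondary endpoints do not fit the common model neatly. One is the "Copenhagen Burnout Inventory (CBI) (Education staff only"). The other is the Workshop Evaluation Measure (WEM), which section 7.1 schedules once, at the third session.

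**The concern.** A mixed ANOVA on the DASS-21 gives a time effect, a group effect and their interaction. The plan names and sizes only the interaction. If the factor is participant type, the interaction asks whether parents and staff change by different amounts, and none of the three hypotheses, the primary objective or the ACT-process question asks that. The change itself is tested by time.

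So if the interaction were taken to decide the primary hypothesis, a workshop that helped parents and staff equally would be reported as having no effect 95% of the time, however large the benefit. If time decided, the same data would often show the fall. An unstated choice that can reverse the primary conclusion, and that could be made after the results are seen, is a fair thing to question.

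The single sentence also cannot apply to every outcome. With staff only, a parent/staff factor has one level, so the CBI has no interaction. The WEM has one measurement, so it has no within-person factor at all.

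**Working it through.** **Inputs from the plan (section 8.1).** Two groups (k = 2), three measurements (m = 3), f = 0.25, alpha 0.05, power 0.80, N = 28, recruitment 40.

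**Assumptions, not in the documents.** Correlation between visits rho = 0.5 (range 0.3 to 0.7), sphericity, the factor being participant type, and the split between parents and staff.

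**Formula.** Noncentrality λ = f² × N × m / (1 − rho). With k = 2 the time effect and the interaction both have m − 1 = 2 and (N − 2)(m − 1) degrees of freedom.

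**Step 1: reproduce the 28.** λ = 0.0625 × 28 × 3 / 0.5 = 10.5, with 2 and 52 df. Power is 0.812. At N = 26 it is 0.778, so 28 is the smallest equal-group total that reaches 0.80. Attrition: 28 / (1 − 12/40) = 40, as stated. The stated figures are right at rho = 0.5.

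**Step 2: does the 28 depend on which effect decides?** No. With two equal groups λ and both df are the same, so f = 0.25 gives 0.81 for time and 0.81 for the interaction. The same f means different things, though. For time it is a fall of 0.53 SD in both types (immediate and sustained). For the interaction it is a difference of 1.06 SD between the two falls.

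**Step 3: what each effect shows when both types fall 0.53 SD.** Time powers are from the formula. Interaction and joint probabilities are from 40,000 simulated studies. For unequal groups N in λ is replaced by 4/(1/n₁ + 1/n₂), which is 21 for 7 and 21.

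| Split | rho | Time significant | Interaction significant |
|---|---|---|---|
| 14 + 14 | 0.3 | 0.66 | 0.05 |
| 14 + 14 | 0.5 | 0.81 | 0.05 |
| 14 + 14 | 0.7 | 0.96 | 0.05 |
| 7 + 21 | 0.3 | 0.53 | 0.05 |
| 7 + 21 | 0.5 | 0.68 | 0.05 |
| 7 + 21 | 0.7 | 0.89 | 0.05 |

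With 14 + 14, time is significant and the interaction is not in 0.77 of studies at rho = 0.5 (0.63 to 0.91 over the range).

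**Step 4: unequal falls.** If one type falls 0.71 SD and the other 0.35 SD (14 + 14, rho = 0.5), f for the interaction is 0.083. Then λ = 0.083² × 28 × 3 / 0.5 ≈ 1.17 and power is 0.14. Time stays at 0.81.

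**Step 5: set the output against the hypotheses.** Running the model in section 8.2 yields the time test in the same analysis as the interaction. The follow-up clause refers to effects in the plural and is not limited to the interaction. The hypotheses speak of reducing distress and burnout and increasing self-efficacy. In the case that causes worry (time significant, interaction not), an analyst following the text would follow up a significant time effect that bears directly on the written hypothesis.

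**Step 6: CBI and WEM.** For the CBI, a parent/staff factor drops out and time in staff is the only effect left, so there is nothing to choose. Its power at f = 0.25 and rho = 0.5 is 0.48 with 14 staff (λ = 0.0625 × 14 × 3 / 0.5 = 5.25; 2 and 26 df). The 0.80 in section 8.1 therefore does not carry over to this secondary outcome, and section 8.1 does not say that it does. For the WEM no repeated-measures model can be fitted, and section 8.2 already provides mean, SD and range for the dependent variables.

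**The case for a change.** The strongest case for a change is that the hypotheses are confirmatory in wording, section 8.1 powers a test at 0.05, and the rule joining test to hypothesis is missing. A literal reader could say that the plan has chosen the interaction, since it is the only effect named in sections 8.1 and 8.2. On that reading the primary hypothesis is tested by something that is null whenever both types benefit equally. Naming the effect would take one sentence and no extra participants.

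Much of this stands as description. The factor and the deciding effect are not written down anywhere, the powers above are correct, and some analytic freedom remains. What does not stand is the step to harm. The interaction phrase can simply describe a mixed model. The loss occurs only if someone reports no effect while holding a significant time result that matches the stated hypothesis.

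The obvious remedy is also not clean. Declaring that time decides would rest a directional hypothesis on an omnibus F test, which a rise in distress could also trigger, as could a fall that has reversed by six weeks. Time is also a before-after comparison without a control, so naming it would not by itself attribute the change to the workshop. An interest in who changes more is not foreign to the study either: section 3 adopts a realist framework about what works for whom, although section 1.1 treats contexts and mechanisms as a qualitative question.

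**Conclusion.** No change follows. Section 8.2 is brief, and it leaves the between factor and the deciding effect unwritten, but no figure in the plan is wrong. The 28 reproduces (power 0.81) and holds for either effect with two groups. Carrying out the plan as written produces the time test that the hypotheses call for, so an equal fall in parents and staff would still show, with probability 0.81 for a 0.53 SD fall with 14 of each type (0.66 to 0.96 for correlations 0.3 to 0.7) and 0.68 with 7 and 21 (0.53 to 0.89). The contrast of 0.81 against 0.05 measures the cost of a misreading, and the plan does not direct that misreading. The CBI and WEM points resolve themselves: staff-only time for the first, descriptive summaries for the second.

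This rests on the factor being parent versus education staff, which is the likely reading and is not stated, and on the assumed correlation, sphericity and split. It also assumes that the analyst reads the time effect with its direction against the written hypothesis, as the wording of the hypotheses invites.
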